7. TRIAL PARTICIPANTS

7.1 Overall Description of Trial Participants

20 patients with acute TIA (within 7 days), and 20 healthy controls will be recruited from the specialist TIA clinic at University Hospitals of Leicester NHS Trust.

TIA participants will be given a minimum of 1 hour, and a maximum of 48 hours to decide whether or not to take part in the study, but must undertake the study assessment within 7 days of their TIA.

Healthy control participants will be given a minimum of 1 hour, and a maximum of 7 days to decide whether or not to take part in the study. There is no time restriction on when they undertake the study assessment.

7.2 Inclusion Criteria

HEALTHY CONTROLS:

- Willing to participate
- Capacity to consent to the study
- Aged over 18 years
- Able (in the Investigator's opinion) and willing to comply with all study requirements
- Good understanding of written and verbal English

TIA PATIENTS:

- Willing to participate
- Capacity to consent to the study
- Aged over 18 years
- Able (in the Investigator's opinion) and willing to comply with all study requirements
- A diagnosis of acute (≤ 7 days) TIA, made by a specialist in the TIA clinic at University Hospitals of Leicester NHS Trust that fulfils the 2009 American Heart Association definition of TIA
- Good understanding of written and verbal English

7.3 Exclusion Criteria

ALL PARTICIPANTS (HEALTHY CONTROLS AND TIA PATIENTS)

- Unwilling to take part
- Unable to consent
- Aged under 18 years
- Unable (in the Investigator's opinion) or unwilling to comply with any study requirements
- Female participants who are pregnant, lactating or planning pregnancy during the course of the study
- A diagnosis of atrial fibrillation
- A diagnosis of severe heart failure (Ejection Fraction $< 30\%$)
- Severe respiratory disease
- Inadequate bilateral transcranial Doppler windows (see section 8.3)
- Carotid stenosis $\geq 70\%$ (unilateral or bilateral)
- Participant enrolled in an interventional research study.
- Poor understanding of written and verbal English

8. STUDY PROCEDURES

8.1 Screening and Eligibility Assessment

Patients attending the specialist TIA clinic at University Hospitals of Leicester NHS Trust will be eligible for recruitment into the study.

Medical records will be reviewed by the direct care team to ensure participants meet the inclusion and exclusion criteria. Eligibility screening will only be undertaken by the direct clinical care team for potential participants.

Participants will be approached at their clinical consultation in the specialist TIA clinic by consultants, registrars or specialist nurses to determine study interest prior to referral to the researcher and provision of study specific information. A poster advertising the study will be displayed in the TIA clinic waiting room. Both participants with TIA, and healthy controls (those without a diagnosis of TIA) will be recruited from the clinic. Healthy spouses, friends or partners of patients with TIA will be asked if they would like to participate in the study as a healthy control subject.

TIA participants will be given a minimum of 1 hour, and a maximum of 48 hours to decide whether or not to take part in the study, but must undertake the study assessment within 7 days of their TIA.

Healthy control participants will be given a minimum of 1 hour, and a maximum of 7 days to decide whether or not to take part study. There is no time restriction on when they undertake the study assessment.

8.2 Informed Consent

We will only invite participants who have capacity to give us consent in this research study. The researcher will have primary responsibility for assessing the capacity of the individual to participate in research, according to the Mental Capacity Act 2005 and under the direct supervision of the Chief Investigator of the project.

Informed consent will be undertaken by [name] in the Cerebral Haemodynamics in Ageing and Stroke Medicine (CHIASM) laboratory located in the Windsor building, Leicester Royal Infirmary.

The participant must personally sign and date the latest approved version of the informed consent form before any study specific procedures are performed. Written and verbal versions of the

CONFIDENTIAL

current approved Participant Information Leaflet (PIS) and Participant Consent Form will be presented detailing no less than: the exact nature of the study; the implication and constraints of the protocol; the known side effects and any risks involved in taking part. It will be clearly stated that the participant is free to withdraw from the study at any time for any reason without prejudice to future care and with no obligation to give the reason for withdrawal. However, should this situation occur the research team would like to keep all the information and data that has been collected so far for the final analysis. This will be clearly stated in both the PIS and Participant Consent Form.

Participants with TIA will be allowed up to 48 hours (minimum of one hour) to consider the information, providing they will still be able to participate in the study within 7 days of their TIA.

Healthy control participants will be given a minimum of 1 hour, and a maximum of 7 days to decide whether or not to take part in the study. There is no time restriction on when they undertake the study assessment.

Participants will be given the opportunity to question the Investigator, their GP or other independent parties to decide whether they will participate in the study. Written Informed Consent will then be obtained by means of participant dated signature and dated signature of the person who presented and obtained the informed consent.

Volunteers will also be allowed up to 48 hours (minimum of one hour) to consider the information, and the opportunity to question the Investigator or other independent parties to decide whether they wish to participate in the study. Written informed consent will then be obtained by means of volunteer dated signature and dated signature of the person who presented and obtained the informed consent.

The person who obtains the consent will be suitably qualified and experienced, and have been authorised to do so by the Chief/Principal Investigator as detailed on the Delegation of Authority and Signature log for the study. The original signed form will be retained at the study site within the Trial Master File (TMF) or Investigator Site File (ISF). A copy of the signed Informed Consent will be given to participants and a copy retained in the participant medical notes.

8.3 TCD window insonation check

Once a consent form has been signed, and before collecting baseline information on demographics and handedness, or undertaking the SSM, participants will undergo a brief Transcranial Doppler

Ultrasound (TCD) check to ensure they have adequate acoustic temporal windows (inadequacy rates of 5-37% well documented in the literature) [Itoh et al 1993, Marinoni et al 1997].

If the participant is found to have inadequate acoustic windows, then they will be unable to participate in the study any further, and will be recorded as a screen failure.

8.4 Collection of demographic data

To avoid repetition and undue burden to participants, consent will be obtained from participants to record the following data from their TIA clinic letter as detailed below:

- Date of birth
- Gender
- Height
- Weight and BMI
- Past Medical History
- Current Medications
- GP name and address
- Smoking status
- Capillary blood glucose
- Carotid ultrasound result
- Type and result of brain imaging

Healthy controls will be asked the above information directly, although will be unable to provide capillary blood glucose, carotid ultrasound or brain imaging results.

- Participants will be asked to detail their ethnicity according to the 18 standardised ethnic categories outlined in the 2011 Office of National Statistics census (Appendix A)
- Handedness will be determined for all participants using the Edinburgh Handedness Inventory [Oldfield 1971] (Appendix B)

8.5 TCD Assessment

For all subjects, all assessments will be undertaken in a dedicated cardiovascular research laboratory at Leicester Royal Infirmary (LRI), which is at a controlled temperature (20-24°C) and is free from distraction. Participants will be asked to refrain from heavy meals, strenuous exercise, alcohol, smoking and caffeine if possible for four hours prior to attending the research laboratory. Baseline brachial casual BP will be measured using a validated UA767 BP monitor. Beat-to-beat non-invasive BP will be recorded continuously using the Finometer cuff device (Finapres Medical Systems; Amsterdam, The Netherlands) attached to the middle finger of the right hand which will be supported in an arm sling. R-R interval will be recorded using a 3-lead electrocardiogram (ECG). Respiratory rate will be recorded, and end-tidal partial pressure of carbon dioxide (EtCO₂) will be monitored using small nasal cannulae placed at the base of the nose (Salter Labs, ref 4000) attached to a capnograph (Capnocheck Plus) to monitor the breathing. A tilt sensor will be attached to the thigh of the participant's right leg by means of a Velcro strap to measure the efficiency and angle of the squatting motion. Simultaneous bilateral insonation of the middle cerebral arteries (MCAs) will be performed using TCD with 2MHz probe using a DWL Doppler box, with the subject either sitting or lying supine on a couch (in the case of difficult to insonate windows). The vessels will be located via the temporal bone window, and identified as the MCAs by their waveform, depth, velocities, and direction of flow. All parameters will be simultaneously recorded onto a computer software system (PHYSIDAS), providing data for subsequent off-line analysis. A head frame will be used to secure the ultrasound probes in position and to minimise their movement. Once satisfactory signals have been obtained, four recordings will be made:

- 1) A 5 minute baseline recording during which the participant sits quietly with their eyes open
- 2) A 6 minute recording during which the participant sits for 1 minute before standing and remaining standing quietly with their eyes open for 5 minutes
- 3) A recording during which the participant is asked to stand for 10 seconds before squatting down and remaining in a squat position for 10 seconds before standing back up and then repeating this process for 5 minutes. A computer program will provide visual cues to the participant to guide the timings of the squat-stand sequence. As each squat manoeuvre (consisting of a squat down and stand back up) will last for 20 seconds, the participant will be required to perform a total of 15 squats in the 5 minute period. This recording will begin and end with a period of 90 seconds baseline recording where the participant stands quietly with their eyes open.

A period of instruction will precede recording 3 during which the SSM will be demonstrated. During squats, participants will be asked to breathe through their nose and to avoid straining if possible. Participants will be instructed to squat down as low as they feel able. They will be informed that they will need to perform a maximum 15 squats and to take this into account when choosing their depth. Participants will be informed that they should try to complete all 15 squats if possible. However, if they wish to stop the SSM before this, they should make the investigator aware during a standing period and ideally remaining standing for a further 90 seconds before being disconnected from the equipment.

During the recordings the internal plethysmography servo-adjust of the Finometer will be switched off, but this will be switched back on in between each recording to allow for accurate calibration of BP. A brachial BP will also be taken in between each recording using the same validated UA767 BP monitor as at the beginning of the baseline assessment.

Participants will be allowed to rest for as long as needed before leaving the laboratory at the end of the study measurement. Refreshments will be provided, and travel expenses will be refunded.

There is a very small chance that the 3 lead ECG could detect a heart abnormality (arrhythmia) in either the healthy controls or the patient participants. Should this situation occur, we would explain our findings to the participant and notify their GP. Formal written consent will be obtained to cover this circumstance.

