Transient ischaemic attack (TIA) is defined as "a transient episode of neurologic dysfunction caused by focal brain, spinal cord or retinal ischemia without acute infarction" [Easton et al 2009]. Approximately 46,000 people in the UK each year have a first TIA [Rothwell et al 2005] and one in 12 people will have a full stroke within a week of having a TIA [Coull et al 2004]. Urgent assessment in a specialist TIA clinic ensures timely and appropriate investigations and rapid interventions (such as antiplatelet therapy, blood pressure-lowering medication, statins, anticoagulation and carotid

endarterectomy or stenting where appropriate) [Rothwell et al 2007]. TIA and acute ischaemic stroke share the same pathophysiological mechanisms and, whilst there have been a significant number of studies investigating cerebral haemodynamics and CA in acute stroke, there have been very few studies exploring CA and TIA. A study by Atkins et al reported no impairment of cerebrovascular haemodynamic control following TIA [Atkins et al 2010]. However, recent abstract level data suggest altered CA is predictive of patients who go on to have further TIAs and strokes [Musthak et al 2017].

Cerebral haemodynamics can be studied using techniques such as functional magnetic resonance imaging (fMRI), positron emission tomography (PET) or single-photon emission computed tomography (SPECT). However, these techniques are expensive, in the case of SPECT involve radiation, and there are feasibility issues including the need to lie still for prolonged periods and to have no metal implants. Transcranial Doppler Ultrasonography (TCD) is a simple, non-invasive imaging modality with high temporal resolution which allows for continuous and bilateral recording of cerebral blood flow velocity (CBFv) through the major cerebral arteries [Aaslid et al, 1982]. TCD has the advantage that CBFv measurements can be made in standing, seated, tilted and supine positions. Continuous measurements of CBFv using TCD have shown that CBFv is affected by perturbations in arterial blood pressure (BP) [Aaslid et al 1989].

The most widely used, validated, modelling technique in the analysis of the relationship between CBFv and BP is transfer function analysis (TFA) [Claassen et al 2016]. TFA makes it possible to examine the effect of changes in (BP) on CBFv. It quantifies the extent to which the input signal, BP, is reflected in the output signal, CBFv, and was first proposed by Giller.

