15. DATA HANDLING AND RECORD KEEPING

15.1 Data Extraction

As supportive evidence of the diagnosis of TIA in TIA participants, results and significant findings from Computerised Tomography (CT) head/Brain Magnetic Resonance Imaging (MRI) and Carotid Ultrasound, if undertaken, will be recorded on the CRF.

Other information which will be extracted from the medical notes of TIA participants and recorded on the CRF include smoking status, capillary blood glucose, medications, past medical history, height, weight and BMI.

The medical notes of healthy control participants will not be reviewed, and participants will instead be asked their smoking status, medications, past medical history, height and weight directly. Answers to these questions will be recorded on the CRF.

Data regarding participants' age, date of birth, ethnicity and handedness will also be recorded onto the CRF. All other parameters, including CBFv, squat angle, heart rate (HR), BP, and ETCO₂, will be recorded onto a computer system (PHYSIDAS), providing data for subsequent analyses.

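### Both MCAs are recorded, but the plan lists neither the symptomatic side nor the territory of the TIA, and gives no rule for using the two signals

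*Combined protocol and SAP*

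**What the plan says.** Section 8.5 plans two-sided recording: "Simultaneous bilateral insonation of the middle cerebral arteries (MCAs) will be performed". Section 7.3 makes inadequate bilateral windows an exclusion, so some people are turned away in order to obtain signals from both sides.

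Section 8.4 says that "consent will be obtained from participants to record the following data from their TIA clinic letter as detailed below". Eleven items follow. The nearest to laterality are the carotid ultrasound result and "Type and result of brain imaging". Section 15.1 takes imaging and carotid findings, where done, as support for the diagnosis. It continues: "Other information which will be extracted from the medical notes of TIA participants and recorded on the CRF include smoking status, capillary blood glucose", followed by medications, past history, height, weight and BMI. Neither list has symptomatic side, vascular territory or presenting symptoms. Handedness is collected for everyone.

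Section 4 defines TIA as arising from "focal brain, spinal cord or retinal ischemia without acute infarction". Section 7.2 adopts the 2009 American Heart Association definition and adds no restriction to the MCA territory.

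Section 11.1 compares TIA participants with HC by two-way ANOVA or the Friedman test. It does not mention hemisphere, affected side, or how left and right values are combined.

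**The concern.** A TIA is a focal event, and the study measures each hemisphere separately. Without the side of the event, left and right can be analysed but affected and unaffected cannot. The obvious choices that ignore side are to average the two MCAs, to use one fixed side, or to test left and right separately. Each mixes affected with unaffected hemispheres. Without the territory, events that an MCA recording may not reflect cannot be identified either.

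The items already listed do not reliably fill the gap. The definition excludes acute infarction, so brain imaging will often not show the side. Section 7.3 excludes carotid stenosis of 70% or more, which removes the clearest one-sided carotid findings.

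The stated hope in section 4 is to learn whether autoregulation is impaired after TIA. The background cites one study that found no impairment and one abstract that suggests altered autoregulation. If this study found no difference, the planned data could not tell absence of impairment from dilution of a one-sided impairment. A hemisphere rule chosen after the data are seen would also leave room for selective reporting.

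**Working it through.** **Inputs from the documents.** 20 TIA and 20 HC (section 2). A cited figure of 11 per group for a 2-unit ARI difference, with 80% power at the 5% level (11.2). No SD, between-hemisphere correlation or combining rule is given.

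**Assumptions.** Two-sided test. The deficit is 2 units in the affected hemisphere and 0 in the other. The correlation r between hemispheres is varied.

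**Step 1: the plan's own figure.** Because 11.2 gives no SD, 11 per group cannot be reproduced independently. It can only be solved for the SD that it implies. With a t test on 20 df, the noncentrality is 2 / (SD × √(2/11)), and power is 80% at SD = 1.59: 2 / (1.59 × 0.4264) = 2.95. The normal formula gives 1.67. A one-sided normal reading gives 1.89.

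**Step 2: affected side analysed, every event lateralised.** Noncentrality = 2 / (1.59 × √(2/20)) = 2 / (1.59 × 0.3162) = 3.98. On 38 df, power is 97%.

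**Step 3: two-side mean, every event lateralised.** The difference becomes (2 + 0) / 2 = 1 unit, and the SD becomes 1.59 × √((1 + r)/2).

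| r | SD of mean | Noncentrality | Power |
|---|---|---|---|
| 1 | 1.59 | 1.99 | 49% |
| 0.8 | 1.51 | 2.10 | 53% |
| 0.5 | 1.38 | 2.30 | 61% |
| 0 | 1.12 | 2.81 | 78% |

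If one fixed side is used and half the patients are affected on that side, simulation gives about 40-42%.

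**Step 4: some events do not lateralise to an MCA.** Here such events carry no deficit and take the two-side mean. The TIA values are compared with the two-side mean in HC by an unequal-variance t test (simulation, SD 1.59, r = 0.8 to 0.5). For the two-side mean in everyone, the difference is the lateralised share × 1 unit, that is 0.8 or 0.6.

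| Share lateralised | Affected-side analysis | Two-side mean for all |
|---|---|---|
| 100% | about 98% | 53-61% |
| 80% | 85-88% | 36-42% |
| 60% | 59-63% | 22-26% |

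The 98% differs slightly from the 97% of step 2 because the HC value is here a two-side mean with smaller variance.

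**Step 5: other SDs, every event lateralised.** Section 4 gives normal ARI as 5 ± 1. If that is read as an SD of 1 (an assumption), the two-side mean has about 87-94% power (r = 1 to 0.5). At SD 1.89 the affected side has 90% (noncentrality 2 / (1.89 × 0.3162) = 3.35) and the two-side mean 37-47% (noncentrality 1.67 to 1.93).

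**The case against.** A reader might infer that the affected hemisphere can never be analysed, or that the plan forces the two sides to be averaged. The documents support neither.

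- Section 8.8 makes medical records the source documents for TIA participants, and the 15.1 list is worded as open. The side may be retrievable later, and both signals will exist. This stands, so the accurate statement is that recording is not planned. Retrieval is not free, however, because 8.4 ties consent to a list that lacks these items.
- Section 11.1 contains no averaging rule. The gap is silence on how the hemispheres are used. This also stands.
- Nothing in the documents says that impairment after TIA is one-sided. The declared comparison is between groups, and the outcomes in 6.2 are counts that dilution does not touch. This stands, and it makes the power loss conditional. It does not justify leaving out the data that would settle the question.
- The SD of 1.59 is back-solved from a cited study which, by its title in section 19, used spontaneous pressure fluctuations and not squat-stands. With an SD of 1 the loss is modest. This stands, and is why a range is shown.
- The 97% is a best case, since it needs every event to have an MCA side. This stands. The affected-side analysis nevertheless remains ahead at each share examined in step 4.

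**Conclusion.** The omission is confirmed. Both sides are measured and required, the side and territory of the event are not listed for recording, and the use of the two signals is not specified. As planned, the dataset would not separate affected from unaffected hemispheres.

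The consequence is conditional. If the deficit is confined to one hemisphere and side is ignored, a 2-unit ARI deficit appears as 1 unit in the two-side mean. At SD 1.59 with every event lateralised, power falls from about 97% to 49-61% (r = 1 to 0.5), or to 78% at r = 0. With fewer lateralised events both analyses lose power. If the SD is nearer 1 the loss is small, and if the impairment is bilateral there is none. It would go too far to infer that the study is bound to miss an effect: the documents give no SD, no correlation and no evidence on laterality.

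The point is worth acting on because the change is cheap and affects what the study can conclude. It contradicts no figure in the plan.

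**What to change.** - **Data collection.** Add symptomatic side and vascular territory, taken from the TIA clinic letter, to 8.4 and 15.1, and to the matching list in the consent documents.
- **Main hemisphere analysis.** In 11.1, pre-specify one value per participant: the affected MCA in TIA participants against the mean of both MCAs in HC. Use an unequal-variance test, because a one-side value and a two-side mean have different variances. A mixed model with hemisphere within subject is an alternative.
- **Default.** Use the two-side mean for events that do not lateralise.
- **Secondary and sensitivity analyses.** Report the unaffected side as secondary. Add an analysis restricted to lateralised carotid-territory TIAs, stating whether retinal events are included.

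The cost is two CRF fields, some wording in 11.1, and a small change to the consent documents that needs approval under 14.5. No visit, measurement or participant is added, and eligibility is unchanged. The drawback is that the default for events with no side mixes two kinds of value within the TIA group, so the report should give the number of each.
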